#### 10.4.8 Interim Analyses

No interim analyses are planned; however, assessments from the Comfort Assessment will be analyzed in a blinded manner to ensure study stopping criteria have not been met and to confirm the dose for the 4 week Safety and Efficacy Assessment. If study stopping criteria have been met, unblinding may be needed to fully assess the data prior to dose selection.

## **11 COMPLIANCE WITH GOOD CLINICAL PRACTICES, ETHICAL CONSIDERATIONS, AND ADMINISTRATIVE ISSUES**

This study will be conducted in compliance with the protocol, Good Clinical Practices (GCPs), including the International Conference on Harmonization (ICH) Guidelines, and in general, consistent with the Declaration of Helsinki. In addition, all applicable local,

state, and federal requirements relevant to the use of study drugs in the countries involved will be adhered to.

## **11.1 Protection of Human Subjects**

### **11.1.1 Subject Informed Consent**

Informed consent/assent must take place before any study specific procedures are initiated. Signed and dated written informed consent must be obtained from each subject and/or from the subject's parent or legal guardian prior to enrollment into the study. If the subject is under the legal age of consent, the consent form must be signed by a legal guardian or as required by state and/or local laws and regulations.

All informed consent/assent forms must be approved for use by the sponsor and receive approval/favorable opinion from an IRB/IEC prior to their use. If the consent form requires revision (e.g., due to a protocol amendment or significant new safety information), it is the investigator's responsibility to ensure that the amended informed consent is reviewed and approved by Ora prior to submission to the governing IRB/IEC and that it is read, signed and dated by all subjects subsequently enrolled in the study as well as those currently enrolled in the study.

### **11.1.2 Institutional Review Board (IRB) Approval**

This study is to be conducted in accordance with Institutional Review Board regulations (U.S. 21 CFR Part 56.103). The investigator must obtain appropriate IRB approval before initiating the study and re-approval at least annually.

Only an IRB/ERC approved version of the informed consent form will be used.

## **11.2 Ethical Conduct of the Study**

This study will be conducted in accordance with the ethical principles that originated with the Declaration of Helsinki.

## **11.3 Subject Confidentiality**

All personal study subject data collected and processed for the purposes of this study should be maintained by the investigator and his/her staff with adequate precautions as to ensure that the confidentiality of the data in accordance with local, state, and federal laws and regulations.

Monitors, auditors and other authorized representatives of Ora, the sponsor, the IRB/IEC approving this study, the FDA, the DHHS, other domestic government agencies, and other foreign regulatory agencies will be granted direct access to the

study subject's original medical and study records for verification of the data and/or clinical trial procedures. Access to this information will be permitted to the aforementioned individuals to the extent permitted by law.

A report of the results of this study may be published or sent to the appropriate health authorities in any country in which the study drug may ultimately be marketed, but the subject's identity will not be disclosed in these documents.

## **11.4 Documentation**

Source documents may include a subject's medical records, hospital charts, clinic charts, the investigator's study subject files, as well as the results of diagnostic tests such as X-rays, laboratory tests, and EKGs. The investigator's copy of the Case Report Forms serves as the investigator's record of a subject's study-related data.

### **11.4.1 Retention of Documentation**

All study related correspondence, subject records, consent forms, record of the distribution and use of all study drug and copies of case report forms should be maintained on file for at least two years after the last approval of a marketing application in an ICH region and until there are no pending or contemplated marketing applications in an ICH region; or until at least two years have elapsed since the formal discontinuation of clinical development of the study drug. These documents will be retained for a longer period if required by the applicable regulatory requirements or by an agreement with the sponsor. It is the responsibility of the sponsor to inform the investigator/institution as to when these documents no longer need to be retained.

If the responsible investigator retires, relocates, or for other reasons withdraws from the responsibility of keeping study records, custody must be transferred to a person who will accept the responsibility. The sponsor must be notified in writing of the name and address of the new custodian.

## **11.5 Labeling, Packaging, Storage, Accountability, and Return or Disposal of Study Drug**

### **11.5.1 Labeling/Packaging**

Investigational drug will be packaged and labeled into clinical kits.

For the Comfort Assessment, subjects will receive one Subject Comfort Kit containing all of the drug needed for dosing. Within the kit will be 3 bottles labeled "Visit 1a", one bottle labeled "Visit 3a", and 3 bottles labeled "Visit 5a". In addition, there will be a Take-Home kit which will contain 15 bottles, enough for 4 days of dosing plus 3 reserve bottles.

For the Safety and Efficacy Assessment, 24 bottles will be packaged in one week clinical kits. One bottle contains enough supply for one dose. The extra bottles in the kit will not be used and will be returned to the clinical site at the next visit. Subjects will receive 2 kits at each visit 2b and 3b.

Further information on the labeling and packaging of study drug can be found in the study Dispensation and Collection Plan.

#### **11.5.2 Storage of Study Drug**

The study drugs must be stored in a secure area accessible only to the investigator and his/her designee(s). Study drug(s) must be refrigerated (2-8°C, Do Not Freeze), protected from light, and secured at the investigational site in a locked refrigerator/room.

#### **11.5.3 Accountability of Study Drug**

The study drugs are to only be prescribed by the principal investigator or his/her named sub investigator(s), and is to only be used in accordance with this protocol. The study drugs must only be distributed to subjects properly qualified under this protocol to receive study drug. The investigator must keep an accurate accounting of the study drugs by maintaining a detailed inventory. This includes the amount of study drugs received by the site, amount dispensed to subjects, amount returned to the site by the subjects, and the amount returned to the Sponsor upon the completion of the study.

#### **11.5.4 Return or Disposal of Study Drug**

All study drugs will be returned to the sponsor or their designee for destruction.

### **11.6 Recording of Data on Source Documents and Electronic Case Reports Forms (eCRFs)**

All subject data will be captured in the subject source documents which will be transcribed in the eCRFs. The investigator is responsible for ensuring that study data is completely and accurately recorded on each subject's eCRF, source documents, and all study-related materials. All study data should also be attributable, legible, contemporaneous, and original. Recorded datum should only be corrected in a manner that does not obliterate, destroy, or render illegible the previous entry (e.g., by drawing a single line through the incorrect entry and writing the revision next to the corrected data). An individual who has corrected a data entry should make clear who made the correction and when, by adding to the correction his/her initials as well as the date of the correction.

Data entry of all enrolled and randomized subjects will use software that conforms to 21 CFR Part 11 requirements, and will be performed only by staff who have been trained on the system and have access to the system. Data will not be entered for screen failure subjects. An audit trail will be maintained within the electronic system to capture all changes made within the eCRF database. After the end of the study and database lock, compact discs (CDs) containing copies of all applicable subjects' eCRFs will be provided to each Investigator Site to be maintained on file by the Investigator.

## **11.7 Handling of Biological Specimens**

Impression cytology samples will be collected from the worst eye at Visits 2b and 4b. Samples will be stored at the site and then submitted to the sponsor upon request for processing, storage and analysis. Details of sample collection, handling, storage, and shipping procedures are found in a study procedure manual.

## **11.8 Publications**

Authorship and manuscript composition will reflect cooperation among all parties involved in the study. Authorship will be established before writing the manuscript. The study sponsor and Ora will have the final decision regarding the manuscript and publication.

## 13 APPENDICES

### Appendix 1: Schedule of Visits and Measurements

**Table 1 Schedule of Visits and Measurements (Comfort Assessment)**

Procedure	Visit 1a (Day 1)	Visit 2a (Day 2)	Visit 3a (Day 3)	Visit 4a (Day 4)	Visit 5a (Day 5)	Visit 6a (Day 6)	Visit 7a (Day 8)	Visit 8a (Day 12)
HIPAA/Informed Consent	X							
Medical / Medication History and Demographic	X							
Medical History Update and Adverse Event Query	X	X	X	X	X	X	X	X
Urine Pregnancy Test 	X							X
Randomization	X							
Visual Acuity Assessment	X	X	X	X	X	X	X	X
Vital Signs	X	X	X	X	X	X	X	X
Slit Lamp Biomicroscopy	X	X	X	X	X	X	X	X
Intraocular pressure (non-contact) Assessment	X	X	X	X	X	X	X	X
Study Drug Dosing or Dispensation/Collection 	X		X		X		X 	X 
On Site Comfort Assessment	X		X		X		X 	
Study Exit								X

For females of childbearing potential.  
Study drug dosing at 0.01% to 0.1% TOP1630 or Placebo, QD or TID.  
Study drug Take Home kit dispensed for at-home dosing on Days 8-11. Take Home kit collected at Visit 8a.  
Comfort Assessment to be done at home on Day 8-11.

**Table 2 Schedule of Visits and Measurements (Safety and Efficacy Assessment)**

Procedure	Visit 1b Day -7 ± 1		Visit 2b Day 1		Visit 3b Day 15 ± 1		Visit 4b Day 29 ± 2	
	Pre CAE®	Post CAE®	Pre CAE®	Post CAE®	Pre CAE®	Post CAE®	Pre CAE®	Post CAE®
Informed Consent / HIPAA	X							
Medical / Medication History and Demographic	X							
Run-in Placebo Collection			X					
Study Drug Collection					X		X	
Diary Collection			X		X		X	
Medical / Medication History Update			X		X		X	
Adverse Event Query	X	X	X	X	X	X	X	X
Pregnancy Test	X 						X 	
Ocular Discomfort – Ora, Calibra® / Dry Eye Symptoms	X	X	X	X	X	X	X	X
OSDI® Questionnaire	X		X		X		X	
Visual Acuity (ETDRS)	X		X		X		X	
Vital Signs	X		X		X		X	
Review of Qualification Criteria	X	X	X	X				
Slit-lamp Biomicroscopy	X	X	X	X	X	X	X	X
VAS Symptom Assessment	X		X		X		X	
Impression Cytology (EyePrim)				X				X
Conjunctival Redness, Ora Calibra® Scale	X	X	X	X	X	X	X	X
Lid Margin Redness, Ora Calibra® Scale	X		X		X		X	
Posterior Lid Edge Evaluation, Ora Calibra® Scale	X		X		X		X	
TFBUT	X	X	X	X	X	X	X	X

Fluorescein Staining-Ora Calibra® and NEI Scale	X	X	X	X	X	X	X	X
Lissamine Green Staining-Ora Calibra® and NEI Scale	X	X	X	X	X	X	X	X
Corneal Sensitivity (Cochet-Bonnet)	X						X	
OPI 2.0			X				X	
Unanesthetized Schirmer's Test	X		X		X		X	
CAE® Exposure		X		X		X		X
CAE® Discomfort – Ora Calibra® Ocular Discomfort Scale		X		X		X		X
Intraocular pressure (non-contact)		X						X
Undilated Fundus Exam		X						X
Run-in Placebo & Diary Dispensation		X						
Randomization				X				
Subject self-instillation of study drug				X		X		
Ora Calibra® Drop Comfort Assessment				X		X		
Study Drug Dispensation				X		X		
Diary Dispensation		X		X		X		
Exit Subject from Study								X
¹For females of childbearing potential.								

## **Visual Acuity Procedures**

This procedure will be performed according to Ora, Inc. SOPs and/or guidance documents.

LogMAR Visual Acuity (VA) must be assessed using an ETDRS chart. The procedure used will be consistent with the recommendations provided for using the ETDRS eye chart. Visual Acuity should be evaluated at the beginning of each visit in the study (i.e., prior to slit-lamp examination). Subjects should use most recent correction to attain their best- corrected visual acuity (BCVA).

### **Equipment**

The visual acuity chart to be used is the ETDRS chart. If smaller reproduction (18" by 18", e.g., from Prevent Blindness) wall charts are used, the subject viewing distance should be exactly 10 feet (or as specified by the manufacturer). In ALL cases, for purposes of standardizing the testing conditions during the study, all sites must use only ETDRS Series 2000 Chart 1 & 2, and the right eye (OD) should be tested first. For reflectance (wall) charts, the chart should be placed frontally and well illuminated.

### **Measurement Technique**

The chart should be at a comfortable viewing angle. The right eye should be tested first. The subject should attempt to read each letter, line-by-line, left to right, beginning with line 1 at the top of the chart. The subject should be told that the chart has letters only, no numbers. If the subject reads a number, he/she should be reminded that the chart contains no numbers, and the examiner should then request a letter in lieu of the number. The subject should be asked to read slowly, so as to achieve the best identification of each letter. He/she is not to proceed to the next letter until he/she has given a definite response.

If the subject changes a response (e.g., 'that was a "C" not an "O"') before he/she has read aloud the next letter, then the change must be accepted. If the subject changes a response having read the next letter, then the change is not accepted. The examiner should never point to the chart or to specific letters on the chart during the test.

A maximum effort should be made to identify each letter on the chart. When the subject says he/she cannot read a letter, he/she should be encouraged to guess. If the subject identifies a letter as one of two letters, he/she should be asked to choose one letter and, if necessary, to guess. When it becomes evident that no further meaningful readings can be made, despite encouragement to read or guess, the examiner should stop the test for that eye. However, all letters on the last line should be attempted as letter difficulties vary and the last may be the only one read correctly. The number of letters missed or read incorrectly should be noted.

### **LogMAR Visual Acuity Calculations**

The last line in which a letter is read correctly will be taken as the base logMAR reading. To this value will be added the number " $N \times 0.02$ " where 'N' represents the total number

of letters missed up to and including in the last line read. This total sum represents the logMAR visual acuity for that eye.

For Example: Subject correctly reads 4 of 5 letters on the 0.2 line, and 2 of 5 letters on the 0.1 line.

Base logMAR	= 0.1
N (total number of letters incorrect on line 0.2 as well as 0.1)	= 4
N x T (T=0.02)	= 0.08
Base logMAR + (N x T)	= 0.1 + 0.08
logMAR VA	= 0.18

Repeat the procedure for the left eye (OS).

In order to provide standardized and well-controlled assessments of visual acuity during the study, all visual acuity assessments at a single site must be consistently done using the same lighting conditions and same correction if possible during the entire study. If the same correction cannot be used (i.e., a subject forgets his/her glasses), the reason for the change in correction should be documented.

Note: A clinically significant visual acuity decrease (defined as an increase of 0.22 or greater in logMAR score) from baseline will be considered an Adverse Event.

## Collection of Vital Signs

Each subject will have vital signs assessments (resting blood pressure, pulse and Oxygen saturation (SpO2)) conducted at each study visit for both the Comfort and Safety and Efficacy Assessment. Vital signs are to be conducted by qualified site staff member delegated by the Principal Investigator.

### **Systolic/ Diastolic Blood Pressure (mmHg)**

Systolic and diastolic blood pressure should be measured in the same arm, when possible, each time using a sphygmomanometer for subjects who have been in a resting state (seated upright) at least 5 minutes. Blood pressure will be recorded in mm Hg.

### **Pulse (bpm)**

Pulse will be measured for subjects who have been in a resting state (seated) for at least 5 minutes. Pulse will be measured using the Pulse Oximeter, and recorded in beats per minute.

### **Oxygen Saturation (Sp O2 %)**

SpO2 will be measured for subjects who have been in a resting state (seated) for at least 5 minutes using the Pulse Oximeter and recorded as a percentage.

### **Slit-lamp Biomicroscopy**

Slit-lamp biomicroscopy will be performed during the study. Observations will be graded as *Normal* or *Abnormal*. Abnormal findings, which are clinically significant, will be described. The following will be examined at each visit:

- **Cornea**
- **Conjunctiva**
- **Anterior Chamber**
- **Iris**
- **Lens**
- **Lid**

External magnification and biomicroscopy will be performed using a slit-lamp. Magnification will be consistent with standard clinical practice. The subject will be seated.

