## 5.2 Study population characteristics

### Inclusion Criteria

Subjects must meet all of the following requirements to be eligible for enrollment into the study:

For the Comfort Assessment:

1. Be at least 18 years of age;
2. Provide written informed consent;
3. Have a patient reported history of dry eye for at least 6 months prior to Visit 1a;
4. Have a history of use or desire to use eye drops for dry eye symptoms for at least 6 months prior to Visit 1a;

For the Safety and Efficacy Assessment:

All of the above criteria (at Visit 1b), and:

5. Report a score of  $\geq 2$  in at least one symptom of the Ora Calibra® Ocular Discomfort & 4-Symptom Questionnaire at Visits 1b and 2b;
6. Report an OSDI® score  $\geq 18$  at Visits 1b and 2b;
7. Have a conjunctival redness score of  $\geq 1$  according to the Ora Calibra® scale in at least one eye at Visits 1b and 2b;
8. Have a tear film break-up time (TFBUT)  $>1$  and  $< 7$  seconds in at least one eye at Visit 1b and 2b;
9. Have a Schirmer's Test score of  $\leq 10$  mm and  $\geq 1$  mm in at least one eye at Visits 1b and 2b;
10. Have a corneal fluorescein staining score of  $\geq 2$  according to the Ora Calibra® scale in at least one region (e.g. inferior, superior, or central) in at least one eye at Visits 1b and 2b;
11. Have a total lissamine green conjunctival score of  $\geq 2$ , based on the sum of the temporal and nasal regions of the conjunctiva according to the Ora Calibra® scale in at least one eye at Visits 1b and 2b;
12. Demonstrate a response to the CAE® at Visits 1b and 2b as defined by:
  - a. Having at least a  $\geq 1$  point increase in fluorescein staining in the inferior region in at least one eye following CAE® exposure on the Ora Calibra® scale; and
  - b. Reporting an Ocular Discomfort score  $\geq 3$  at 2 or more consecutive time points in at least one eye during CAE® exposure on the Ora Calibra® scale (if a subject has an Ocular Discomfort rating of 3 at time = 0 for an eye, s/he must report an Ocular Discomfort rating of 4 for two consecutive measurements for that eye).

13. Have at least one eye (the same eye) satisfy all criteria for 7, 8, 9, 10, 11, and 12 above;
14. At Visit 2b, subjects must have at least 5 days' worth of diary symptom data and deemed by the PI to be 80% compliant with vehicle eye drops.

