### **Exclusion Criteria**

Subjects may not participate in the study (Comfort Assessment as well as the Safety and Efficacy Assessment) if any of the following criteria are met:

1. Unable or unwilling to follow instructions, including participation in all study assessments and visits;
2. Have any clinically significant slit lamp findings at Visit 1 (1a or 1b) that may include active blepharitis, meibomian gland dysfunction (MGD), lid margin inflammation or active ocular allergies that require therapeutic treatment, and/or in the opinion of the investigator may interfere with study parameters;
3. Be diagnosed with an ongoing ocular infection (bacterial, viral, or fungal), or active ocular inflammation at Visit 1 (1a or 1b);
4. Have any significant ocular lesion that could interfere with assessment of safety or efficacy or prevent study conduct in the opinion of the PI;
5. Have worn contact lenses within 14 days of Visit 1 (1a or 1b) or anticipate using contact lenses during the study;
6. Have used any eye drops within 2 hours of Visit 1 (1a or 1b);
7. Have previously had laser-assisted *in situ* keratomileusis (LASIK) surgery within the last 12 months or any other ocular surgeries within the last 6 months;
8. Have used Restasis® or Xiidra™ within 90 days of Visit 1 (1a or 1b);
9. Have used topical ocular steroids within 30 days of Visit 1 (1a or 1b);
10. Have any planned ocular and/or lid surgeries over the study period;
11. Have temporary punctal plugs at Visit 1 that have not been stable within 45 days of Visit 1 (1a or 1b) or anticipate having temporary punctal plugs inserted during the study;
12. Have had punctal occlusion (not including punctal plugs) within 6 months of Visit 1(1a or 1b);
13. Be currently taking any topical ophthalmic prescription (including medications for glaucoma) or over-the-counter (OTC) solutions, artificial tears, gels or scrubs, and cannot discontinue these medications for the duration of the trial (excluding medications allowed for the conduct of the study) or have used any of these medications in the previous 24 hours prior to visit 1 (1a or 1b);
14. Have corrected visual acuity greater than or equal to logMAR+0.7 as assessed by Early Treatment of Diabetic Retinopathy Study (ETDRS) scale in both eyes at Visit 1 (1a or 1b);
15. Have an uncontrolled systemic disease;
16. Be a woman who is pregnant, nursing or planning a pregnancy;

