9.1 Unit of Analysis

Safety endpoints will be analyzed for both eyes. For efficacy endpoints, the unit of analysis will be the "worst eye" as defined by the following:

Worst Eye: Eyes are eligible for analysis if they meet all of the inclusion criteria. In the case that both eyes are eligible for analysis, the study eye will be the eye with worse (higher) increase in total corneal staining change from pre-CAE® to post-CAE® at Visit 2b on the Ora Calibra® scale. If the increase in total corneal staining is the same in both eyes, then the study eye will be the eye with the largest increase in ocular discomfort from pre-CAE® to post-CAE® at Visit 2b. If the ocular discomfort symptom increase is the same in both eyes, then the right eye will be selected as the worst eye.

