13.2 Treatment Exposure

For the Safety and Efficacy Assessment, extent of exposure will be calculated in days using the following:

Extent of Exposure (days) = [Date of last dose – Date of Visit 2b (Day 1)] + 1

Extent of treatment exposure (days) for each subject exposed to study drug will be summarized with continuous descriptive statistics for each treatment group, using the Safety population. A subject listing of treatment exposure will also be produced.

14. Safety Analyses

Frequencies and percentages of subjects with treatment-emergent adverse events (TEAEs), serious TEAEs, and TEAEs causing discontinuation will be provided by treatment group. An AE is treatment emergent if it occurs or worsens after the first dose of study treatment. Furthermore, frequencies will be given of subjects with TEAEs by SOC and PT; by SOC, PT and maximal severity; by SOC and PT for treatment-related AEs; by SOC, PT for SAEs; and by SOC, PT, and time of onset. Separate summaries will be provided for ocular specific and all AEs (including systemic).

Other safety endpoints including VA, slit-lamp biomicroscopy, corneal sensitivity, undilated fundoscopy, IOP (non-contact), and vital signs will be summarized by treatment group, visit, and time point (where relevant) using descriptive statistics. Changes or shifts from baseline will also be summarized where appropriate. For assessments performed by eye, study eye and fellow eye will be summarized separately. In addition, shifts from baseline to worst on-treatment value for ocular safety assessments will be summarized.

Safety variables will be summarized as appropriate. All safety analyses will be performed on the Safety population. No statistical inferential testing will be performed for safety variables.

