14.3 Slit-Lamp Biomicroscopy Examination

Slit-lamp biomicroscopy examinations will be conducted on both eyes at all scheduled visits, Pre- and Post-CAE®. The slit lamp findings will include examinations of the cornea, conjunctiva, anterior chamber, iris, lens and lid. Each parameter will be graded as normal or abnormal. Abnormal findings will be further classified as not clinically significant (NCS) or clinically significant (CS).

Slit lamp findings will be summarized by treatment group and visit, for the worst eye and fellow eye separately, using qualitative summary statistics (frequency counts and percentages). Percentages will be based on the number of subjects with non-missing values for the treatment group at a given visit.

A shift table will show changes from baseline (Visit 2b (Day 1), Pre-CAE®) to all observations at later study visits and time points. The data for slit lamp biomicroscopy will be presented in a listing.

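### Slit-lamp safety for cornea and conjunctiva rests on a coarse grade, and no listed safety table shows graded worsening of conjunctival redness or corneal staining, by eye, on the Safety population

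*Protocol*

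**What the plan says.** **Slit-lamp grade.** Protocol Appendix 2 (Slit-lamp Biomicroscopy) uses two levels, Normal and Abnormal: "Abnormal findings, which are clinically significant, will be described". SAP 14.3 begins the same way, "Each parameter will be graded as normal or abnormal", and then divides Abnormal into NCS and CS, which makes three levels. The visible text gives no criteria for CS. Findings are summarised for worst eye and fellow eye separately, and "A shift table will show changes from baseline (Visit 2b (Day 1), Pre-CAE®) to all observations at later study visits and time points". SAP 14 adds that "shifts from baseline to worst on-treatment value for ocular safety assessments will be summarized".

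**Entry criteria (Protocol 5.2).** At Visits 1b and 2b a subject needs conjunctival redness >=1, corneal fluorescein staining >=2 in at least one region and a total lissamine green conjunctival score >=2. Criterion 13 ties these to a single eye: "Have at least one eye (the same eye) satisfy all criteria for 7, 8, 9, 10, 11, and 12 above". Exclusion criterion 2 covers clinically significant slit-lamp findings at Visit 1.

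**Graded scales.** Protocol Appendix 1 (Table 2) and SAP 4.2 schedule conjunctival redness and fluorescein staining before and after CAE at all four visits. Protocol 6.2 and SAP 3.2 list both as exploratory efficacy measures; Protocol 6.1 and SAP 3.1, the safety lists, contain neither. SAP 9.1 says "For efficacy endpoints, the unit of analysis will be the" worst eye. In SAP 21 the fluorescein tables (14.2.1.1 to 14.2.2) and the redness table (14.2.7) are efficacy tables on mITT or PP. Safety tables 14.3.1.1 to 14.3.9 include no staining or redness table.

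**The concern.** Safety and tolerability are the primary objective of a first-in-man topical drug, and cornea and conjunctiva are the tissues the drop touches. A study eye that enters with staining and redness may well start at Abnormal-NCS on the slit lamp. From there the only recordable worsening is the step to CS, which is a judgement. An eye that becomes clearly worse without reaching CS is recorded as unchanged.

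The scales that could show such a change feed only the efficacy tables. A minority of eyes that worsen can be offset there by benefit in the others, and the planned tests compare arms on the whole distribution. The worst on-treatment shift does not reach these scales, because it covers safety assessments and they are not listed as such. The fellow eye is dosed too, yet the visible text plans no summary of its staining or redness.

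**Working it through.** **1. The plan's own safety figure.** Protocol 10.3 and SAP 6 give a 79% probability of detecting an AE with a 5% rate in either arm. With 30 per arm, 1 - 0.95^30 = 0.785, so the figure reproduces as the chance of at least one event per arm. (With n = 60 it would be 0.954.)

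**2. What a coarse baseline does to that figure.** The share of study eyes graded Abnormal at baseline is not given, so it is varied here. If m eyes per arm start Normal, the chance of seeing at least one Normal-to-Abnormal shift at a 5% rate is 1 - 0.95^m:

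| Abnormal at baseline (assumed) | m of 30 | Chance of >=1 shift |
|---|---|---|
| 0% | 30 | 78.5% |
| 50% | 15 | 53.7% |
| 80% | 6 | 26.5% |
| 90% | 3 | 14.3% |
| 100% | 0 | 0% |

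This loss concerns Normal-to-Abnormal shifts only. Eyes that start at NCS can still move to CS.

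**3. What the planned efficacy comparison would show.** Assumptions: 30 per arm, normally distributed changes, positive = worse, placebo mean 0; 20,000 simulated trials, two-sided alpha 0.10.

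- Case A: SD 0.6; 4 active subjects worsen by 2 grades, 26 improve by 0.3. Mean difference = (4 x 2 - 26 x 0.3)/30 = 0.2/30 = 0.007 grade. The t-test flags worsening in 1.3% of trials. The median difference is -0.19, in favour of active.
- Case B: 3 worsen by 2 grades, the rest do not change. Mean difference = 6/30 = 0.2. Worsening is flagged in 23% of trials at SD 0.6 and 18% at SD 0.8.

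**4. What a count at a single look would show (Case A).**

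- >=1 grade, active: 4 x P(Z >= -1.67) + 26 x P(Z >= 2.17) = 3.81 + 0.39 = 4.2. Placebo: 30 x P(Z >= 1.67) = 1.4.
- >=2 grades, active: 4 x P(Z >= 0) = 2.0, plus a negligible term. Placebo: 30 x P(Z >= 3.33) = 0.01.

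**5. What a worst-of-many-looks count would show (Case A).** Assume 3 corneal regions x 2 visits x pre/post = 12 looks, with the four harmed subjects worse by 2 grades at every look. Expected subjects per 30, active vs placebo:

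| Correlation between looks (assumed) | >=1 grade | >=2 grades |
|---|---|---|
| 0.3 | 7.5 vs 9.9 | 3.9 vs 0.1 |
| 0.5 | 6.8 vs 7.9 | 3.7 vs 0.1 |
| 0.7 | 6.0 vs 5.8 | 3.4 vs 0.1 |

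The >=1-grade count loses the signal or reverses it; the >=2-grade count keeps it. The 4.2 vs 1.4 of step 4 belongs to one look and does not carry over to a worst-value rule.

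**The case against.** **Safety outputs do count worsening.** A reader might infer that no safety output counts eyes that got worse. The documents contradict that. The SAP plans slit-lamp and fundoscopy shift tables, shifts to the worst on-treatment value, a tabulation of acuity loss of 10 letters or more, and an IOP threshold that makes a rise an AE. Under Protocol 9.1 an unfavourable sign, or a pre-existing condition that worsens after dosing, is an AE; ocular AEs are tabulated by arm on the Safety population. What stands is narrower: none of these outputs reports graded redness or staining.

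**The ceiling is an inference.** A reader might also infer that Normal-to-Abnormal shifts in cornea and conjunctiva are impossible. No text links a redness or staining score to the slit-lamp grade. At Visit 2b the slit-lamp examination is listed before that visit's dyes, so a stained-cornea score does not oblige the examiner to have called the undyed cornea Abnormal. The redness scale is not visible. SAP 14.3 leaves the NCS-to-CS step, and the entry criteria bind only one eye. This objection stands in full.

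**More than means is planned.** SAP 16 includes SD, median, minimum, maximum and Wilcoxon tests, and SAP 22 includes listings. In Case A the SD of change averages 0.99 vs 0.59 and the maximum +2.6 vs +1.2, so a careful reader of the efficacy table could notice the outliers. That is a real mitigation, but it gives no number of worsened subjects per arm and does not cover the fellow eye.

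**Missing text.** Parts of SAP 16.1 to 16.3 and 16.5 cannot be read, so a worst-eye count there cannot be excluded. The visible safety lists in SAP 3.1 and 21 do not depend on that text.

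**Conclusion.** The point holds in a limited form. Slit-lamp safety for cornea and conjunctiva uses two levels in the Protocol and three in the SAP, and deterioration within Abnormal-NCS is recorded as no change. How many eyes this affects is unknown: probably many study eyes, not necessarily all, and fellow eyes are not constrained by entry. The finer scales are already in use but are classed only as efficacy, so no listed safety table shows their worsening on the Safety population, and none in the visible text covers the fellow eye.

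The size can only be illustrated. Under the assumed SDs and effects, the efficacy t-test flags minority worsening in 1.3% to 23% of trials. Those inputs are not in the documents, and the normal model is an approximation for ordinal grades. The illustration supports adding a count. It does not show that harm would go unseen, since AEs, listings and maxima remain.

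**What to change.** Add one descriptive table to SAP 14 and to the safety tables in SAP 21, and name the two measures in SAP 3.1:

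- Safety population, by arm, study eye and fellow eye separately.
- Conjunctival redness, and corneal fluorescein staining by region.
- Distribution of change from the time-point-matched Visit 2b value, with number and percentage worsening by >=1 and by >=2 grades, at each post-baseline visit and time point.
- The number of subjects with an observed value as denominator. Protocol 8.3.1 asks only for safety evaluations at early termination, so some early leavers may have no grade.
- If a worst on-treatment row is included, the >=2-grade count printed beside the >=1-grade count.

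Cost: SAP wording and one more table, with no new visits or tests. SAP 16.1 states that staining is graded in both eyes; the corresponding text for redness is cut, so post-baseline collection by eye should be confirmed against the eCRF. The downside is that grading noise will produce some worsening in both arms, which must be read against placebo.
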